### Sample Size Determination / Power Analysis

The primary foci of this study are amount of breast milk expressed after initiation and time to lactogenesis II. For the continuous longitudinal outcome amount of breast milk expressed, with 60 subjects randomized to each intervention group (early, intermediate, late initiation), we will have 85% power to detect at least a 0.5 standardized (sd units) effect size between the three intervention groups [assuming 13 time points (initial expression, days 1-7, 14, 21, 28, 35, 42)]; intra-class correlation no greater than 0.5; level of significance ( $\alpha$ )=0.02, two-tailed ]. A standardized effect size of 0.49sd (Cohen's d, "moderate" effect) is equivalent to a raw effect size of 125 ml (raw scale units) for expressed breast milk (assuming pooled sd for expressed breast milk is 250, from preliminary data. For number of hours to achieve lactogenesis II assuming  $\alpha$  = 0.02 (Type I error rate), two-sided; independent sample t-test comparison of means (adjusted for multiple comparison between 3 groups); equality of variance between groups with 60 mothers per group we will have 85% power to detect a difference of 34.1 hours (effect size  $\Delta$ =0.62s;  $s$ =55.0) between the groups.

For analysis of the continuous secondary efficacy outcome measure self-efficacy, we will have 85% power to detect a difference of 0.62 s between the three groups assuming  $\alpha$  = 0.02 (Type I error rate), two sided; independent sample t-test comparison of means; equality of variance between groups accounting for multiple comparisons.

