#### Design/Analysis Issues.

Analysis sets. For primary analyses the intent-to-treat (ITT) sample will be used comprising all randomized mothers patients. Secondary per-protocol (completer) analysis will include mothers who were compliant with protocol requirements and for whom all required measurements have been made. ITT and per-protocol analyses will be compared to test the sensitivity of our conclusions to non-adherence/attrition.

Missing data. Every attempt will be made by the study coordinator to keep mothers in the study, with the help of the student research team members and to obtain required measurements in order to ensure the completeness of the study data. To minimize potential bias due to missing observations, mothers will be contacted by phone if vials of expressed breast milk are missed, and reasons for missing data will be carefully documented. Subject participation will only be terminated due to safety reasons for mother and infant, withdrawal of consent, or loss to follow-up. Several approaches to handle missing data in the ITT analysis set will be employed. For continuous variables using a single end-of-study value (e.g., amount of milk expressed at day 42), Little and Rubin's multiple imputation methods will be used (Little & Rubin, 1997). For analyses of longitudinal outcome data, we will use longitudinal methods (e.g. mixed models) capable of dealing with missing data (Hedeker & Gibbons, 2006).

Multiple outcome variables. In order to address possible Type I errors due to the number of outcome variables, we specify the primary outcome measures a priori corresponding to the stated a priori hypothesis and maintain the alpha (significance) level at 0.02. For analysis of secondary outcome variables, we will further adjust resulting p-values using Bonferroni-type corrections for multiple outcomes. Both unadjusted and adjusted p-values will be reported.

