### **Analyses for Aim 1**

The primary efficacy outcomes are amounts of breast milk expressed over the first 7 days post-initiation; days 14, 21, 28, 35, and 42 days post-initiation and weekly, and number of days to achieve lactogenesis stage II. To examine expressed breast milk amount over time (i.e. production of breast milk immediately after initiation and subsequently, volume measured daily over the first 7 days and on days 14, 21, 28, 28, and 42 post-initiation and weekly), we will compare the longitudinal profile of milk volume expressed in the three groups over the

study period using mixed effects models (MEM) analyses. These analyses will estimate the average change in breast milk volume within each group (early vs. immediate vs. late initiation) and individual change in breast milk volume for each mother. MEM analyses allow for missing data, measurement of study subjects at different time points during the study, and time varying covariates. MEM can also take into account the effect of clustering, i.e. correlation of repeated breast milk measurements within one subject (Hedeker & Gibbons, 2006; McCulloch & Searle, 2001). The efficacy variable expressed breast milk volume (mL) will be used as the dependent variable with treatment status (early vs. intermediate vs. late initiation), time and time-by-treatment interaction and gestational group (23-27 weeks vs. 38-32 weeks) as primary independent variables. In a second step, additional covariates will be included in the models to adjust for putative predictive variables such as age, mother's weight at delivery, diagnosis of preeclampsia or diabetes, parity, birth weight, weeks of gestation, behavioral factors including skin-to-skin contact ("kangaroo care"), lactation support and mean number of pumping attempts per day. Effect modifications of covariates will be examined through inclusion of a covariate-by-treatment interaction term in the multivariable models. For example, a significant age-by-treatment interaction would suggest that the relationship between treatment and milk volume is different for older mothers compared to younger mothers. Potential key intervening variables such as behavioral factors will be further examined using mediation analysis. Further, the relationship of maternal mood with amount of breast milk will be examined by inclusion of the MAACL-R scores obtained at discharge, days 21 and 42 in the longitudinal MEM model.

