Additionally, unadjusted mean differences in volume of breast milk at day 1 through 42 will first be compared overall via one-way ANOVA (or equivalently non-parametric Kruskal-Wallis tests) between the three groups. Subsequently, pooled t-tests will be used to compare unadjusted means pairwise between the groups (using significance level  $\alpha = 0.02$  to account for multiple comparisons). Mean differences for volume of breast milk at day 1 through 42 and number of days to achieve lactogenesis stage II will be adjusted for gestational group (strata) and putative covariates such as age, mother's weight at delivery, diagnosis of preeclampsia or diabetes, parity, birth weight, weeks of gestation, behavioral factors including kangaroo care and lactation support. Mean number of pumping attempts per day will be compared for each outcome measure (as dependent variable) using a general linear model (GLM) approach for the three milk initiation groups.

Furthermore, survival distribution for time from delivery to lactogenesis stage II will be obtained for each group using the Kaplan-Meier product limit method, and will be compared using the logrank test. Cox proportional hazards regression modeling (PHM) will be used with time from delivery to lactogenesis stage II as the dependent variable, and treatment (early vs. moderate vs. late initiation) and gestational group (strata) as the primary independent variables. Additional covariates and interaction terms will be added as described above for MEM analyses.

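### Daily tests of milk volume at 0.02 allow for three arm pairs but not for 12 measured days, so a false difference on some day has a chance of about 15% to 35%

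*Combined protocol and SAP*

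**What the plan says.** Analyses for Aim 1 makes expressed milk volume a primary outcome, with "volume measured daily over the first 7 days" and then weekly. Its lead analysis is a mixed effects model with treatment, time and their interaction. As an addition, the section says that "unadjusted mean differences in volume of breast milk at day 1 through 42 will first be compared overall via one-way ANOVA", with Kruskal-Wallis as the alternative. It continues: "Subsequently, pooled t-tests will be used to compare unadjusted means pairwise between the groups", at 0.02, which it describes as the allowance for multiplicity. It gives no level for the ANOVA and no rule that a non-significant ANOVA stops the pairwise tests.

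The power section lists "13 time points (initial expression, days 1-7, 14, 21, 28, 35, 42". Leaving out the initial expression, that is 12 days between day 1 and day 42. The power section ties the adjusted level to comparisons among the three groups.

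Under Design/Analysis Issues, the paragraph on multiple outcomes says that the plan will "maintain the alpha (significance) level at 0.02" for primary outcomes. It keeps Bonferroni-type correction for secondary outcomes.

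**The concern.** A level of 0.02 is close to 0.05 divided by three pairs, so it allows for the three arm comparisons on one occasion. Repeating those comparisons on 12 days gives the same outcome 12 overall tests and 36 pairwise tests. No sentence in the plan controls error across days, and the correction for secondary outcomes does not reach a primary outcome.

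The tests stand under the primary aim, use the primary significance level and are not called descriptive, supportive or exploratory. A report that follows the plan could therefore present one significant day as a finding on a primary outcome, with a false-positive risk well above what 0.02 suggests.

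**Working it through.** **Inputs**
- Level 0.02, two-sided (power section: "0.02, two-tailed"; same level under Design/Analysis Issues).
- Three arms of 60 mothers (power section).
- Days 1–7, 14, 21, 28, 35 and 42: 7 + 5 = 12. The list in Analyses for Aim 1 prints day 28 twice and omits day 35; the count follows the power section.
- Correlation between a mother's measurements: "intra-class correlation no greater than 0.5". This is a ceiling. Inflation falls as correlation rises, so 0.5 gives the smallest inflation in the planned range.
- Assumptions beyond the documents: normal data, equal correlation between all days, no missing values.

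**The plan's own figure.** For lactogenesis the plan states 85% power for 34.1 hours with SD 55.0. Effect size: 34.1/55.0 = 0.62. Normal approximation: Φ(0.62 × √(60/2) − 2.326) = Φ(1.07) = 0.858; the noncentral t gives 0.849. The figure reproduces with 0.02 as the level of a single pairwise test.

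**One day.** Bonferroni bound for three pairs: 3 × 0.02 = 0.06. Simulated chance of any false pair: about 0.053. If pairs are tested only after an ANOVA significant at 0.02: about 0.02.

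**Twelve days, independence formula.** For 12 ANOVAs, 1 − (1 − 0.02)^12 = 0.215. For 36 pairwise tests, 1 − (1 − 0.02)^36 = 0.517, which is too high because pairs share arms.

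**Twelve days, simulation.** 20,000 null trials per setting, Monte Carlo standard error at most about 0.0035. Chance of at least one false day-specific arm difference:

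| Correlation | Gated by ANOVA at 0.02 | Gated by ANOVA at 0.05 | No gate |
|---|---|---|---|
| 0 | 0.219 | 0.428 | 0.483 |
| 0.3 | 0.190 | 0.369 | 0.418 |
| 0.5 | 0.162 | 0.309 | 0.346 |
| 0.8 (above the ceiling) | 0.094 | 0.181 | 0.210 |

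Other runs at 0.5 gave about 15% gated and 34–35% ungated.

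**Inflation, same rule in numerator and denominator.** At correlation 0.5: gated 0.162/0.02 = 8.1; ungated 0.346/0.053 = 6.5. At correlation 0: 0.219/0.02 = 10.9 and 0.483/0.053 = 9.1.

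**False results favouring early expression.** Counting only days on which the early arm is significantly higher than the intermediate or late arm (8,000 null trials), the rate at correlation 0.5 is 6.4% gated at 0.02, 11.8% gated at 0.05 and 13.5% ungated. At correlation 0 it is 9.2% (gated at 0.02) and 20.7% (ungated); at 0.8 it is 3.6% and 7.4%.

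**After correction.** Each ANOVA at 0.02/12 = 0.0017 has a bound of 12 × 0.0017 = 0.02 across days; simulation gives about 1.5% at correlation 0.5 and 2.0% at 0. If all 36 pairs are tested without a gate at 0.05/36 = 0.0014, the chance of any false pair is 0.039 at correlation 0.5 and 0.046 at 0.

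**The case against.** The strongest reply is that these tests are supplementary. The mixed model comes first, the power calculation for volume is longitudinal, the day tests are introduced as an addition, and the Expected Outcomes section speaks of milk produced overall. No sentence says that one significant day would support an efficacy claim. This stands, and it limits the weight of the point. It does not remove it, because the plan never says the day tests are descriptive.

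A second reply is that the order of ANOVA first and t-tests afterwards implies a gate. That is a fair reading, but the plan states neither the gate nor its level. A strict gate at 0.02 still leaves 15–16%.

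A third reply is that the phrase covering day 1 to day 42 may mean one average. Aim 2 under Analyses for Exploratory Aims uses similar words for a mean over six weeks. Here, however, the differences are placed at the days, and the missing-data paragraph gives volume at day 42 as an example of a single-value analysis. The per-day reading is the more natural one, but it remains a reading.

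A reader might also infer that false findings are up to about 17 times likelier than the plan states (0.346/0.02). The documents do not support this. They state no familywise rate for day-specific tests, and that ratio sets an error rate over 36 tests against a level for one comparison that already allows for three pairs.

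**Conclusion.** The point holds in this form: if each measured day is tested, nothing controls error over 12 days. At the plan's correlation ceiling of 0.5, the chance of at least one false day-specific arm difference is about 15–16% with a gate at 0.02 and about 34–35% without one. The matching one-day rates are about 2% and 5%, so the inflation is about 8-fold and 6.5-fold. The rates rise to 22% and 48% at zero correlation, and fall to 9% and 21% at 0.8.

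A reader might take 35% as the chance of wrongly reporting that early expression raised volume. It is not: it counts any arm difference in either direction. The rate for a false result in favour of the early arm is about 6% (gated) to 14% (ungated). Nor do the figures bear on the mixed-model comparison, which these tests only supplement.

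The conclusion rests on the per-day reading, 12 days, complete data from 60 mothers per arm, normality and equal correlation. The covariate-adjusted repeats of the same comparisons are not counted.

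**What to change.** In Analyses for Aim 1, do one of the following.

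- State that the mixed model is the confirmatory analysis of volume and that day-specific ANOVA and t-test results are descriptive estimates with confidence intervals. This is the simpler choice.
- Or require Holm or Bonferroni adjustment across the 12 days before a difference is claimed on any day. For example, test each ANOVA at 0.02/12 and make pairwise comparisons only on days when it is significant. Hold the pairs to that same level, so that control does not depend on all three arms being equal.

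Either way, say whether the ANOVA is a gate and at what level, and reconcile the two lists of measurement days. If a single 42-day average was intended, say so; the repetition over days then disappears.

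The cost is SAP wording only. The downside is that single-day differences become harder to claim.

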### Randomization

Table 1. Randomization and Stratification of Mothers

Gestational Age	Group 1 Early Expressers	Group 2 Intermediate Expressers	Group 3 Late Expressers
23-27 weeks	0-60 minutes	61-180 minutes	181-360 minutes
28-32 weeks	0-60 minutes	61-180 minutes	181-360 minutes

mothers into groups. Following the birth of an infant weighing less than 1500 grams, with a gestational age between 23-32 weeks, mothers who continue to meet inclusion criteria will be stratified according to the gestational age of the infant (23-27 weeks and 28-32 weeks). Gestational age will be determined through one of the following; 1st or 2nd trimester ultrasound or the average of the obstetric gestational age and the results of the Ballard exam. This stratification is based upon likely differences in breast milk production in mothers who deliver earlier in gestation due to decreased mammary gland development and decreased levels of prenatal hormones necessary for preparation of the breast for lactation.

Following stratification, mothers will be randomly assigned to one of three groups to begin milk expression at different time periods following delivery. Group 1 (early expressers) will begin milk expression 0-60 minutes following delivery, Group II (intermediate expressers) will begin 61-180 minutes following delivery, and Group III (late expressers) will begin 181-360 minutes following delivery. The selection of the time periods for the groups is based upon our preliminary data showing greater milk volume and earlier lactogenesis stage II in women who began milk expression within 1 hour following delivery compared to those who began milk expression 1-6 hours following delivery (Parker et al., in press).

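### The log-rank test and the unadjusted comparisons of means omit the gestational-age stratum used in randomisation; if that stratum is prognostic and balanced across arms, they give up some power

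*Combined protocol and SAP*

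**What the plan says.** **Design.** Under Randomization, after delivery "mothers who continue to meet inclusion criteria will be stratified according to the gestational age of the infant", in two bands (23-27 and 28-32 weeks), and are then assigned to one of three arms. The reason given is prognostic: milk production is expected to be lower after earlier delivery. No size is given for that effect, and no blocking or other balancing method within strata is stated.

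**Tests without the stratum (Analyses for Aim 1).**
- Time to lactogenesis II: Kaplan-Meier curves by arm, "and will be compared using the logrank test".
- Milk volume: unadjusted means "compared overall via one-way ANOVA (or equivalently non-parametric Kruskal-Wallis tests) between the three groups", followed by pairwise pooled t-tests at 0.02.

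**Analyses with the stratum (same section).**
- The mixed model for volume and the Cox model for time to lactogenesis II both have gestational group among their primary independent variables.
- Mean differences in volume and in days to lactogenesis II are adjusted for gestational group together with a list of other covariates.

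**Error rate and planning.** Design/Analysis Issues says the plan will "maintain the alpha (significance) level at 0.02" for the primary outcomes. The power section sizes hours to lactogenesis II on a t-test without covariates: "85% power to detect a difference of 34.1 hours", with SD 55.0 and 60 mothers per group. No section says which analysis of time to lactogenesis II is confirmatory.

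**The concern.** When randomisation balances a prognostic factor across arms, the true sampling variance of the treatment contrast no longer contains the between-stratum part. A test that omits the factor still counts that part in its error term. Its p-values then tend to be too large, and it has less power than a test that uses the factor. For the log-rank test there is a second effect: mixing strata with different hazards weakens the separation of the arm curves.

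Two features of the plan make this more than a matter of style. First, the log-rank test and the Cox model stand side by side for a primary outcome with neither named as decisive. They could disagree only because one uses the stratum and the other does not. Second, the pairwise t-tests carry their own significance threshold, so they read as inferential rather than descriptive.

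**Working it through.** **1. The plan's own figure.** Inputs from the power section: 60 per group, difference 34.1 h, SD 55.0, two-sided alpha 0.02.

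Standardised difference: 34.1/55.0 = 0.62. Noncentrality: 0.62 × √(60/2) = 3.396. Normal approximation: power = Φ(3.396 − 2.326) = Φ(1.070) = 85.8%. The exact noncentral t gives 84.9%. The stated 85% is reproduced, and it is already the power of a t-test that ignores the stratum.

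**2. Means: what omitting the stratum costs.** Assumptions: total SD held at 55, strata split 50:50 and balanced across arms, and strata differing by D within-stratum SDs. The stratum then explains R² = (D²/4)/(1 + D²/4) of the variance. By normal approximation:
- actual size, unadjusted = 2 × [1 − Φ(2.326/√(1 − R²))]
- power, unadjusted = Φ((3.396 − 2.326)/√(1 − R²))
- power, adjusted = Φ(3.396/√(1 − R²) − 2.326)

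For D = 1.0, R² = 0.25/1.25 = 0.20 and √0.80 = 0.894. Size is 0.9%, and power is Φ(1.196) = 88.4% unadjusted and Φ(1.471) = 92.9% adjusted. Simulation with t-tests (40,000 runs) gives slightly lower power:

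| D | Gap in hours, D × 55√(1 − R²) | R² | Size, unadjusted | Power, unadjusted | Power, adjusted | Gain (points) |
|---|---|---|---|---|---|---|
| 0 | 0 | 0 | 1.9% | 84.9% | 84.9% | 0 |
| 0.3 | 16.3 | 0.022 | 1.7% | 84.9% | 85.5% | 0.6 |
| 0.5 | 26.7 | 0.059 | 1.6% | 85.5% | 87.0% | 1.6 |
| 0.8 | 40.9 | 0.138 | 1.2% | 86.7% | 90.3% | 3.6 |
| 1.0 | 49.2 | 0.200 | 1.0% | 87.3% | 92.1% | 4.8 |

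A split of one third to two thirds gave similar results. In SD units the table applies equally to a t-test on volume at a 0.62 SD difference.

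**3. Log-rank test.** Three-arm test at 0.02, 30 mothers per arm per stratum. Assumed: exponential times, arm hazard ratios 1.9, 1.35 and 1, and censoring at 168 h. None of these effects is in the documents. There were 20,000 runs for size and 8,000 for power.

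| Stratum HR | Size, plain | Size, stratified | Power, plain | Power, stratified | Loss (points) |
|---|---|---|---|---|---|
| 1 | 2.1% | 2.1% | 77.7% | 77.0% | none |
| 1.5 | 2.1% | 2.3% | 75.6% | 77.8% | about 2 |
| 2 | 1.4% | 2.2% | 70.6% | 78.4% | about 8 |
| 3 | 1.0% | 2.3% | 59.7% | 78.6% | about 19 |

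Simulation standard errors are about √(0.02 × 0.98/20,000) = 0.1 point for size and √(0.75 × 0.25/8,000) = 0.5 point for power. The stratified test ran slightly above 2%, so a small part of each power gap reflects that. With no stratum effect, stratifying costs less than one point.

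**4. If arms are not balanced within strata.** Under simple randomisation, with D from 0.5 to 1.0, the unadjusted t-test keeps a size of about 2% and power of about 85%. The conservatism therefore depends on balance.

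**The case against.** The strongest reply is that the plan already does most of what is asked. The mixed model and the Cox model include gestational group from their first step, and the adjusted means include it too. The ANOVA and t-tests are openly labelled unadjusted and are introduced as additional to the mixed model. Reporting unadjusted and then adjusted results is ordinary practice.

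This largely stands, and it rules out the inference that the plan ignores its strata. It leaves two gaps. The log-rank test has no stratified counterpart and no stated rank relative to the Cox model. The adjusted mean comparison is not a clean substitute for the t-tests, because it combines the stratum with factors that arise after randomisation, such as kangaroo care and help with lactation. For volume on individual days and for mean time to lactogenesis II, no planned comparison adjusts for the stratum alone.

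A second reply is that the size of the effect is unknown. That stands. The Randomization section expects a difference in milk production but says nothing about time to lactogenesis II, which is what the log-rank test examines. A stratum gap of 1.0 SD (49.2 h) would exceed the 34.1 h treatment difference for which the trial was sized. At a stratum hazard ratio of 1.5 the log-rank loss is only about 2 points, and its size is not visibly below nominal.

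**Conclusion.** The point holds as a conditional loss of efficiency. The log-rank test and the unadjusted comparisons of means omit the factor by which the trial randomises. If gestational age is prognostic and the arms are balanced within strata, the log-rank test loses about 2, 8 and 19 points of power at assumed stratum hazard ratios of 1.5, 2 and 3. Its actual size is then about 2.1%, 1.4% and 1.0% against 2%. The t-test forgoes about 0.6 to 5 points for stratum differences of 0.3 to 1.0 within-stratum SD. The stratum effects, arm hazard ratios, exponential times, censoring time and equal strata are all assumptions.

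Three stronger readings are not supported:
- **That the t-test falls short of its planned power.** The trial was sized on an unadjusted t-test, and power stays at about 85% or above if 55 is the total SD. Only an available gain is forgone.
- **That the tests are certainly conservative.** This needs a prognostic stratum and balance within strata. The plan gives no effect size and no balancing method.
- **That a reported hazard ratio will be diluted.** The log-rank test reports none, and the only planned hazard model includes gestational group.

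Any error is towards caution, not false positives, so the validity of the trial is not in question.

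**What to change.** In Analyses for Aim 1:
- Specify a log-rank test stratified by gestational group (23-27, 28-32 weeks), and state whether it or the Cox model is confirmatory for time to lactogenesis II.
- For comparisons of means, make a linear model with arm and stratum only the inferential test, or a van Elteren-type test if a non-parametric method is needed.
- Keep the unadjusted ANOVA and t-tests if wanted, labelled as supportive. Keep the model with post-randomisation covariates as a separate, secondary step.

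The cost is one line of SAP text and one model term, with no new data. If the stratum turns out not to be prognostic, the simulations show essentially no loss from including it.
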